- All other non-injected lesion(s) that are not treated with CyPep-1 injection.
- For Phase I Cohort 3 and all Phase IIa arms, in addition to iRECIST, (exploratory) ORR in injected and non-injected lesions will be assessed per itRECIST ([Appendix F](#)). For Phase I Cohort 3, Phase IIa Arms A, B, and C, data will be extracted retrospectively from eCRF.

Upon start of CyPep-1 treatment, subjects will be followed for PFS (every 8 weeks) and OS. PFS will be radiologically assessed at the trial sites until disease relapse or progression (based on all lesions), death due to any cause, withdrawal of consent, loss to follow-up, or until the end of the trial, whichever occurs first. A phone call for survival status (OS) will be done every 3 months after confirmation of PD and until the end of the trial.

Confirmation of clinical progressive disease:

In order to account for the possibly delayed onset of CyPep-1 action and for subjects who are of acceptable clinical performance status (as deemed by the investigator), if PD is recorded and provided that the tumor enlargement is smaller than 50% compared to the previous measurement, the subject will remain in the trial and will be reassessed radiologically after 4 weeks. All lesion(s) are to be evaluated for clinical progression:

- If the lesion(s) continue(s) to enlarge, the original PD will be considered as the “first documented PD” and there will be an End of Treatment (EoT) visit.
- If lesion(s) remain(s) unchanged or decrease(s) in size, assessments should continue as per protocol (i.e., the next radiological assessment will be performed after an 8-week interval). In this case, the first measured PD will be disregarded.

In case of unconfirmed PD after the first (or subsequent) 3 Q2W injections of CyPep-1, the subject should continue Q2W administrations (start of another cycle of CyPep-1) until confirmed PD. If PD is confirmed 4 weeks later, then the subject will be taken off-trial and move to the EoT visit.

PHARMACOKINETIC ASSESSMENTS:

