4.2 Exclusion Criteria

For Phase I and Phase IIa Arms A, C, and D: Subjects who meet ANY of the following criteria at screening will be excluded from trial entry:

1. There is no limit to the number of prior treatment regimens, but prior treatment(s) should not include compounds delivered by IT injection to the to-be injected lesion(s), including investigational agents. Subjects with prior IT therapies are allowed in Arm D.
2. Participation in another clinical trial within 4 weeks prior to first dose of CyPep-1.
3. Anti-cancer therapy within 4 weeks prior to the first dose of CyPep-1 (within 2 weeks for palliative radiotherapy, within 1 week for endocrine therapy).
4. Major surgical procedure within 14 days prior to the first dose of CyPep-1.
5. Live vaccine within 30 days prior to first dose of CyPep-1.
6. Expected to require any other form of systemic or localized antineoplastic therapy while in this trial. Localized palliative radiotherapy for pain relief is allowed on tumor lesions that are not selected for evaluation of treatment response.
7. Clinical evidence of an active second malignancy that is progressing or requires active treatment, except for curatively treated early stage (carcinoma *in situ* or stage 1) carcinomas or non-melanoma skin cancer.
8. Active autoimmune disease requiring immunosuppressive therapy.
9. Any condition requiring continuous systemic treatment with either corticosteroids (> 10 mg daily prednisone equivalents) or other immunosuppressive agents within 2 weeks prior to first dose of CyPep-1. Inhaled, intranasal or topical (only on areas

outside the injected lesion[s]) and physiological replacement doses of up to 10 mg daily prednisone equivalent are permitted in the absence of active auto-immune disease.

10. Abnormal or clinically significant coagulation parameters.:

- Prothrombin Time – International Normalized Ratio (PT-INR) $\geq 1.5 \times$ ULN
- Activated Partial Thromboplastin Time (APTT) $\geq 1.5 \times$ ULN

Subjects being treated with anticoagulants are excluded if the coagulation parameters are outside the therapeutic intervals as described in the SmPC for the administered treatment.

11. Subjects on anticoagulants with temporarily stop and start, supported by low molecular weight heparin (or other anticoagulation therapy at the discretion of the investigator and/or per local standard of care) during treatment period.

12. Known hypersensitivity to any component of CyPep-1.

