5.6.2 Prohibited Medication and Other Treatments

Medications or vaccinations specifically prohibited in the exclusion criteria are not allowed during the ongoing trial. If there is a clinical indication for any medication or vaccination specifically prohibited during the trial, discontinuation from study intervention or vaccination may be required. The investigator is to discuss prohibited medication/vaccination with the Sponsor's Clinical Director. The final decision on any supportive therapy or vaccination rests with the investigator and/or the participant's primary physician. However, the decision to continue the participant on study treatment requires the mutual agreement of the investigator, the Sponsor and the participant.

The following treatments must not be administered during the trial:

- Immunotherapy not specified in this protocol, immunosuppressive drugs (that is, chemotherapy or systemic corticosteroids except for short-term treatment [≤ 1 week] of allergic reactions or for the treatment of immune-related AEs), or other investigational agents other than CyPep-1 or pembrolizumab, with the exception that COVID-19 treatments are allowed after consultation with the Sponsor and the Medical Monitor. Steroids with no or minimal systemic effect are allowed.
- Chronic concurrent therapy with antibiotics is prohibited within 2 weeks before and during the treatment period.
- Herbal remedies with immunostimulating properties (for example, mistletoe extract) or known to potentially interfere with major organ function (for example, hypericin).
- Any other anti-neoplastic systemic chemotherapy, biological treatment or concurrent anticancer treatment or chemotherapy not specified in this protocol
- Radiation therapy, with the exception of palliative short course, limited-field radiotherapy (ie, ≤ 10 fractions and $\leq 30\%$ bone marrow involvement or per institutional standard), which may be administered during the trial.
- Live or live attenuated vaccines, including live or live attenuated COVID-19 vaccines.

- Systemic glucocorticoids are permitted only for the following purposes:
 - To modulate symptoms of an AE that is suspected to have an immunologic etiology
 - As needed for the prevention of emesis
 - Premedication for IV contrast allergies
 - Short-term oral or IV use in doses >10mg/day prednisone equivalent for COPD exacerbations
 - For chronic systemic replacement not to exceed 10 mg/day prednisone equivalent

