Appendix D: Description of the iRECIST Process for Assessment of Disease Progression

iRECIST is based on RECIST 1.1 but adapted to account for the unique tumor response seen with immunotherapeutic drugs. iRECIST will be used by the investigator to assess tumor response and progression, and to guide decisions about changes in management.

Assessment at Screening and Prior to RECIST 1.1 Progression

Until radiographic disease progression based on modified RECIST 1.1, there is no distinct iRECIST assessment.

Assessment and Decision at RECIST 1.1 Progression

For participants who show radiological PD by RECIST 1.1, the Investigator will decide whether to continue a participant on study treatment until repeat scans are obtained, as described in Section 14.

Tumor flare may manifest as any factor causing radiographic progression per RECIST 1.1, including:

- Increase in the sum of diameters of target lesion(s) identified at baseline to $\geq 20\%$ and ≥ 5 mm from nadir
 - Note: The iRECIST publication uses the terminology “sum of measurements”, but “sum of diameters” will be used in this protocol, consistent with the original RECIST 1.1 terminology.
- Unequivocal progression of non-target lesion(s) identified at baseline
- Development of new lesion(s)

iRECIST defines new response categories, including iUPD (unconfirmed progressive disease) and iCPD (confirmed progressive disease). For purposes of iRECIST assessment, the first visit showing progression according to RECIST 1.1 will be assigned a visit (overall) response of iUPD, regardless of which factors caused the progression.

At this visit, target and non-target lesions identified at baseline by RECIST 1.1 will be assessed as usual.

New lesions will be classified as measurable or non-measurable, using the same size thresholds and rules as for baseline lesion assessment in RECIST 1.1. From measurable new lesions, up to 10 lesions total (up to 2 per organ), may be selected as New Lesions – Target. The sum of diameters of these lesions will be calculated and kept distinct from the sum of diameters for target lesions at baseline. All other new lesions will be followed qualitatively as New Lesions – Non-target.

Assessment at the Confirmatory Scans

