Evaluable lesions	1. Treatment response in injected lesions can be evaluated separately from non-injected lesions 2. Injected lesions remain evaluable for overall response assessment even after termination of local procedures. 3. Excisional tumor biopsy renders a lesion non-evaluable. (Core needle biopsy would not render a lesion non-evaluable but its use is discouraged for target lesions). When feasible, biopsies should be restricted to non-target lesions.	Treatment response is evaluated as a combination of injected and non-injected lesions.

[figure not shown]
Reclassification of Lesions After Baseline	
Injected lesions may change to non-injected lesions and vice versa based on individual circumstances judged per investigators, as long as target lesions always remain target and nontarget lesions remain non-target. However, once any T-NI lesion is injected, the non-injected response becomes non-evaluable.
 
Note: Lesions designated T-NI at baseline should remain non-injected for as long as possible to allow assessment of maximal systemic response to IT therapy in non-injected lesions.
	Reclassification not allowed.
--	--	-------------------------------

Table 2. Difference in Response Assessment between itRECIST and iRECIST

Difference in Response Assessment	itRECIST	iRECIST
Overall Response	Similar to RECIST 1.1, with the difference only in allowing more target lesions, in injected lesions not becoming non-evaluable, and allowing ultrasound assessment.	Per RECIST 1.1
Injected Response and Non-injected Response	
 Injected response is based entirely on the changes in the sum of diameters (SOD) of the targeted-injected (T-I) lesions Non-injected response is based entirely on the changes in the SOD of the targeted-non-injected (T-NI) lesions. Response from non-targeted lesions are not taken into account (See Figure 1) 	Per RECIST 1.1, Target lesion response is based on the combination response of T-I and T-NI lesions, while nontarget lesion response is based on the combination response of NT-I and NT-NI.

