13.2 APPENDIX 2. CENSORING RULES: DOR and PFS

Censoring rules for DOR and PFS are presented in [Table 8](#) below.

Table 8. Censoring Rules for DOR and PFS

#	Situation	Date of Event (PD/Death) or Censoring	Outcome: Event (PD/Death) or Censored
1	No (or inadequate) baseline tumor assessments and the subject has not died	Treatment Start Date	Censored
2	No post-baseline assessments and the subject has not died	Treatment Start Date	Censored
3	iUPD followed by discontinuation due to clinical disease progression, radiological disease progression or death within 8 weeks	Date of assessment of progression ¹	Event
4	iUPD without subsequent iSD, iPR or iCPD and followed by:	Date of assessment of progression ¹	Event
	1. Treatment discontinuation due to clinical instability (i.e., clinical disease progression, radiological disease progression). 2. No further response assessments (due to subject refusal, protocol non-compliance, or subject death). 3. Next timepoint responses all equal to iUPD. 4. Subject death from cancer.		
5	No iUPD as described in #3 and #4, no iCPD or death and no new protocol excluded anticancer treatment documented	Date of last 'adequate' assessment of response ²	Censored
6	No iUPD as described in #3 and #4, no iCPD or death and new protocol excluded anticancer treatment documented	Date of last 'adequate' assessment of response ² on or prior to starting anticancer therapy	Censored
7	New protocol excluded anticancer treatment started (prior to iUPD as described in #3 and #4, iCPD or death) ³	Date of last 'adequate' assessment of response ² on or prior to starting anticancer therapy	Censored
8	iCPD documented between scheduled visits	Date of assessment of progression ¹	Event
9	Death before first iCPD assessment	Date of death	Event
10	Death between adequate assessment visits	Date of death	Event
11	Death or progression after two missed visits (with 1-week window) where last assessment is not iUPD	Date of last 'adequate' assessment of response ² prior to missed assessments	Censored

¹The earliest of

- (i) Date of radiological assessment showing new lesion (if progression is based on new lesion); or
- (ii) Date of radiological assessment showing unequivocal progression in non-target lesions, or
- (iii) Date of last radiological assessment of measured lesions (if progression is based on increase in sum of measured lesions).

²An adequate assessment is defined as a radiological assessment where iCR, iPR, or iSD was determined.

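### SAP Appendix 5 has no irradiation rule for itRECIST response, and Protocol 5.6.2 omits the lesion limit on palliative radiotherapy that 4.2 states

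*Protocol*

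**What the plan says.** **Protocol, on-study rule.** The prohibited list in 5.6.2 includes "Radiation therapy, with the exception of palliative short course, limited-field radiotherapy". The exception is bounded by fractions and marrow involvement, or by institutional standard. It says nothing about which lesion may be treated. The opening of 5.6.2 carries entry restrictions into the trial, but names only drugs and vaccines: "Medications or vaccinations specifically prohibited in the exclusion criteria are not allowed during the ongoing trial".

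**Protocol, entry rule.** Exclusion item 6 (Phase I, Arms A, C and D) and item 30 (Arm B) in 4.2 exclude a subject "Expected to require any other form of systemic or localized antineoplastic therapy while in this trial". Both then add: "Localized palliative radiotherapy for pain relief is allowed on tumor lesions that are not selected for evaluation of treatment response".

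**SAP, derivation.** Section 10.2.1 sends the itRECIST derivation to Appendix 5.
- For non-injected target lesions (T-NI), the only exits there are a lesion that cannot be measured or one that has been injected.
- For injected target lesions (T-I), best response and maximum reduction use each lesion's smallest size after injection, with no end date.

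**SAP, stops stated elsewhere.** Section 10.1.1 ends iRECIST best overall response at confirmed progression or new anticancer therapy. Table 2 in 8.6 gives the same end for maximum reduction in tumor measurements. Section 9.4.3 identifies on-study anticancer procedures by an eCRF tick box.

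**A nearby precedent.** Protocol Appendix F already removes a lesion after another local procedure: "Excisional tumor biopsy renders a lesion non-evaluable". It does not mention radiation.

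**The concern.** The itRECIST analysis exists to separate the local effect of injection from the effect on distant lesions. If a non-injected target lesion is irradiated for pain and shrinks, Appendix 5 followed alone would report that shrinkage as non-injected response. If an injected target lesion is irradiated, its post-radiation size can become the minimum used for best response. In either case a local radiation effect would be credited to CyPep-1.

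The trial is open-label and response rests on investigator assessment. If no rule is fixed beforehand, the handling of such a subject would be decided after the response is known.

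**Working it through.** **1. The plan's own figure.** The only stated figure tied to an itRECIST endpoint is Protocol Table 6: one-sided 90% Clopper-Pearson lower bounds for injected-lesion ORR with n = 30. The formula is the 0.10 quantile of Beta(x, 30 − x + 1). For x = 1 to 9 it gives 0.35, 1.79, 3.73, 5.94, 8.34, 10.86, 13.48, 16.20 and 18.99%. All nine agree with the table to one decimal, and nothing below changes them.

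**2. The rules side by side.**

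| Rule | Limited by lesion? | Stops at new therapy? | Names irradiation? |
|---|---|---|---|
| Protocol 4.2, items 6 and 30 | Yes | n/a | Yes |
| Protocol 5.6.2 | No | n/a | Yes |
| SAP 10.1.1 (iRECIST best response) | n/a | Yes | No |
| SAP 8.6, Table 2 (maximum reduction) | n/a | Yes, unless stated otherwise | No |
| SAP Appendix 5 (itRECIST) | n/a | Not stated | No |

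**3. When one irradiated T-NI lesion can produce itPR.** Assume k equal lesions, with the others unchanged. If one shrinks by a fraction s, the sum falls by 100·s/k %. The threshold is 30%, so the lesion must shrink by 30k %: 30% if it is the only one, 60% if one of two, 90% if one of three. With four, even disappearance gives only 100/4 = 25%.

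**4. The T-I case is easier to reach,** because each lesion contributes its own minimum. Illustration with assumed 20 mm lesions, sizes chosen to sit on the threshold:
- Two lesions, the other's minimum 18 mm. Without radiation: (20 + 18 − 40)/40 = −5.0%, itSD. With the first irradiated to 10 mm: (10 + 18 − 40)/40 = −30.0%, itPR, even if the second has regrown by then.
- Three lesions, the others' minima 16 mm. Without radiation: (20 + 16 + 16 − 60)/60 = −13.3%. With the first irradiated to 10 mm: (10 + 16 + 16 − 60)/60 = −30.0%.

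**5. Effect of one false responder on the reported rate** (two-sided 95% Clopper-Pearson, no true responders):
- Arm B, n = 15: 0% (0 to 21.8) becomes 6.7% (0.2 to 31.9).
- Cohort 3 plus Arm A, n = 24: 0% (0 to 14.2) becomes 4.2% (0.1 to 21.1).

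**6. How often.** The documents give no radiotherapy rate. Assume that 1%, 2% or 5% of Phase IIa subjects have a target lesion irradiated. N runs from 9 + 15 + 9 + 1 = 34 to 18 + 15 + 9 + 1 = 43 (Arms A, B, C, and D as recruited). Expected cases are N·r and the chance of at least one is 1 − (1 − r)^N.

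| Assumed rate | Expected cases | Chance of at least one |
|---|---|---|
| 1% | 0.34 to 0.43 | 28.9 to 35.1% |
| 2% | 0.68 to 0.86 | 49.7 to 58.1% |
| 5% | 1.70 to 2.15 | 82.5 to 89.0% |

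These are chances of an irradiated target lesion, not of a false response. A false response also needs enough shrinkage, few lesions in the set, and no stop applied. SAP 4.3 adds itRECIST for the Phase I cohorts, which would raise N somewhat.

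**The case against.** The strongest reply is that the SAP already covers this. Section 10.2.1 refers the summary of itRECIST ORR back to the iRECIST method, and that method stops at new anticancer therapy. Table 2 is a general rule, and silence in Appendix 5 need not override it. Data collection is also bounded: PFS imaging after early departure ends at further anticancer treatment (Protocol Table 1, footnote 4), as does Arm B imaging after discontinuation (6.2).

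Much of this stands. A reader might infer that itRECIST has no new-therapy stop at all; the documents do not support that, because the cross-reference can fairly be read to import one. The gap is narrower:
- Section 10.2.1 refers back for the summary but sends the derivation to Appendix 5, which defines its own best response and maximum reduction. The T-I rule is a per-lesion minimum, not a ranking of timepoints, so the 10.1.1 window does not transfer automatically.
- Even if the stop carries over, nothing says that permitted palliative radiotherapy triggers it. Section 9.4.3 counts prior radiation, including palliative, as an anticancer procedure, which favours ticking the on-study box, but no on-study rule requires it.
- A subject who has palliative radiotherapy and stays on CyPep-1 continues to be scanned every 8 weeks, so the collection limits do not reach that subject.

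A reader might also infer that 5.6.2 permits irradiating evaluated lesions. Items 6 and 30 speak of therapy during the trial, so the protocol read as a whole points the other way. Both lists are, however, applied at screening, and 5.6.2 is the section a site would consult on study.

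Part of SAP Section 10 before 10.1 is missing from the text available, and lesion guidance also sits in the Study Procedural Manual. The absence of any rule therefore cannot be fully confirmed.

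**Conclusion.** The point holds as a minor one. Protocol 5.6.2 and 4.2 are inconsistent on which lesions may be irradiated. Appendix 5, as written, neither excludes an irradiated target lesion nor says when new therapy ends the data. Radiation shrinkage could therefore be counted as injected or non-injected response.

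The size is limited. Injected and non-injected ORR are exploratory endpoints (Protocol 2.2.3). Cases are probably rare, and the rates above are assumptions. Arm D, the arm sized on injected-lesion ORR, stopped after one subject (SAP 6.1, footnote 1). Procedures are listed and deviations are reviewed before lock, so cases can be found; what is missing is a stated rule for analysing them.

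A reader might infer that PFS, duration of response and duration of stable disease should also be censored at radiotherapy, because the relevant row of SAP Table 8 reads "New protocol excluded anticancer treatment started (prior to iUPD as described in #3 and #4, iCPD or death" and the excluded treatments are not defined. That step is not supported. If the irradiated lesion was growing, the censoring would be informative and could itself lengthen these times.

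**What to change.** 1. **SAP Appendix 5, irradiated lesions.** In Table 11, add *or has been irradiated* to the T-NI non-evaluable row. Treat a T-I lesion as non-evaluable from the start of radiotherapy to it. For both sets, post-radiation sizes should not enter timepoint response, best response or maximum reduction. Responses reached before radiotherapy stay.
2. **SAP Appendix 5, stop.** State that assessments after confirmed progression or the start of new anticancer therapy do not count, as in 10.1.1 and Table 2.
3. **Protocol 5.6.2.** Restrict the palliative exception to lesions outside the response assessment, using the wording of items 6 and 30.
4. **Listing.** Flag subjects who received radiotherapy in the response listing. Add no new censoring for PFS, duration of response or duration of stable disease.

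The SAP changes are a few lines and should be settled before database lock. Sites must record which lesion was irradiated, and reported itRECIST ORR may be slightly lower.

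The protocol clause has a real cost. The synopsis follows for efficacy "All other non-injected lesion(s) that are not treated with CyPep-1 injection", so few lesions may fall outside the response assessment. Under the closing rule of 5.6.2, a subject who needs radiotherapy to an evaluated lesion would have to stop study treatment. Items 6 and 30 already set the lesion limit but attach no such consequence.

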5.6.3 Rescue Medications & Supportive Care

Subjects should receive appropriate supportive care measures as deemed necessary by the treating investigator. Suggested supportive care measures for the management of AEs with potential immunologic etiology are outlined along with the dose modification guidelines in Section 5.3.6 for pembrolizumab.

Note: If after the evaluation of the event, it is determined not to be related to pembrolizumab, the investigator does not need to follow the treatment guidance. Refer to Table 3 in Section 5.3.6.3 for guidelines regarding dose modification and supportive care.

It may be necessary to perform conditional procedures such as bronchoscopy, endoscopy, or skin photography as part of evaluation of the event.

